13.4. Enrollment, Baseline and Pre-ablation

When a patient and the Principal Investigator or authorized designee, as required, have signed and dated the PIC Form, the patient is considered a subject enrolled in the study. The date the subject signed the PIC Form and Authorization to Use and Disclose Personal Health Information/Research Authorization/other privacy language as required by law must be documented in the subject's medical records.

The baseline visit can be a standalone visit or can be performed on the same day but prior to the cryoablation procedure. The following evaluations will be performed after consent, unless previously performed as part of routine clinical evaluations within the specified windows:

Within 6 months prior to consent date:

- Trans-thoracic echocardiogram (TTE) for the collection of left atrial size, left ventricular ejection fraction, and mitral valve impairment. A repeat TTE procedure for the purpose of the study after the consent date is not required if a TTE was performed within 6 months of the consent date and all data are available.

Within 30 days prior to consent date:

- 12-lead ECG and physical exam. A repeat 12-lead ECG and physical exam for the purpose of the study after the consent date is not required if a 12-lead ECG and physical exam were performed within 30 days of the consent date and all data are available.

After consent date but prior to procedure:

Note: The time between the consent date and the procedure should not exceed 30 days.

- Final assessment of all factors specified for evaluation under Inclusion Criteria and Exclusion Criteria (Section 11)
- Demographics
- Medical history
- Pregnancy screen (female subjects of child bearing potential only)
- Review of AF and anticoagulation medications
- SF-12 health survey and AFEQT Questionnaire
- Transesophageal Echocardiogram (TEE)

- When performed, the TEE should occur within one day (on the day of or within the day prior to) the planned ablation procedure.
- A TEE should be performed in all subjects with atrial fibrillation more than 48 hours in duration or of an unknown duration if adequate systemic anticoagulation has not been maintained for at least 3 weeks prior to the ablation procedure.
- Performance of a TEE in subjects who are in sinus rhythm at the time of ablation or eligible subjects that have been in AF for 48 hours or less prior to AF ablation may be considered but is not mandatory.
- The subject will not proceed with the study ablation procedure and will be exited from the study if a left atrial thrombus is visualized.
- [REDACTED] if enrolled in the sub-study (see Appendix B)

13.5. Procedure

Perform the pulmonary vein isolation procedure using Arctic Front Advance Cardiac CryoAblation Catheter. If needed, a Freezor *MAX* Cardiac CryoAblation Catheter may also be utilized for gap ablation to complete electrical isolation of the pulmonary veins and creation of ablation lines between the inferior vena cava and the tricuspid valve. The Investigator is to perform the procedure according to the procedural steps in this CIP and the Instructions for Use for the Arctic Front Advance and Freezor *MAX* Cardiac CryoAblation Catheters. Appropriate sedation and venous access should be attained at the Investigator's standard practice according to their institution's pre-established procedures/guidelines at the time of the procedure. Current recommendations for anticoagulation are found in the 2012 HRS/EHRA/ECAS Expert Consensus Statement on Catheter and Surgical Ablation of Atrial Fibrillation¹, 2014 Focused Update on the Canadian Cardiovascular Society Guidelines for the Management of Atrial Fibrillation¹⁸ and Guidelines for indications and procedural techniques of catheter ablation.¹⁹

Only the Medtronic FlexCath sheath family should be used with the Arctic Front Advance Cardiac CryoAblation Catheter. The use of other sheaths may damage the device. The Investigator may choose compatible guidewires and mapping catheters at his or her discretion.

¹⁸ Verma, A, MD, et al. 2014 Focused Update of the Canadian Cardiovascular Society Guidelines for the Management of Atrial Fibrillation. *Canadian Journal of Cardiology*. 30 (2014) 1114-1130.

¹⁹ Okumura. Guidelines for indications and procedural techniques of catheter ablation. *Japan Circulation Society*. 2012.

13.5.1. Esophageal Visualization and Temperature Monitoring

- a. Ensure an esophageal temperature monitor is used for each cryoablation application. Cease cryoablation if the temperature reaches $\leq 15^{\circ}\text{C}$.

13.5.2. Peri-procedural Anticoagulation

- a. Heparin should be administered prior to or immediately following transeptal puncture during AF ablation procedures and adjusted to achieve and maintain an ACT of 300 to 400 seconds or per standard center guidelines.
- b. Performance of AF ablation in a subject systemically anticoagulated with warfarin or novel oral anticoagulants (NOACs) does not alter the need for intravenous heparin to maintain a therapeutic ACT during the procedure.
- c. Administration of protamine following ablation to reverse heparin should be considered.

13.5.3. Diaphragm Movement

- a. Continuous phrenic nerve pacing must be performed for all right sided pulmonary vein cryoapplications and should be considered for all cryoapplications. Additional methods of phrenic nerve monitoring are recommended.

13.5.4. Balloon Pulmonary Vein (PV) Cryoablation

- a. Every effort consistent with subject welfare should be made to treat all PVs or their anomalous equivalents.
- b. The Arctic Front Advance will be advanced into the left atrium over the Achieve catheter or guidewire and inflated. Once inflated, the catheter will be tracked over the Achieve catheter or guidewire and positioned at the entrance of the PV.
- c. Assess the positioning, contact and occlusion of the PV by the catheter's balloon by injection of contrast material, ultrasound imaging, or other technique. Reposition as needed.
- d. Each pulmonary vein should be minimally assessed for entrance block and, where assessable, exit block to demonstrate electrical isolation.
- e. It is recommended that the Investigator use cryoapplications of three (3) minutes each. Once PV isolation has been achieved, one (1) additional application of three (3) minutes at the same PV should be performed; however, it is up to the operator's discretion to assess application time and necessity of a bonus freeze given factors such as time to isolation of first application, temperature of first application, risk of collateral damage, etc.
- f. Upon the Investigator's assessment of procedure completion, Isoproterenol and/or adenosine may be used to assess pulmonary vein isolation.

13.5.5. Other Ablations during Index Procedure

- a. Ablation of the cavotricuspid isthmus, with the goal of achieving bi-directional isthmus block, is required for subjects with a history of typical atrial flutter or inducible cavotricuspid isthmus dependent atrial flutter. It is recommended to attempt an induction of cavotricuspid isthmus dependent atrial flutter if the subject does not have a history of this arrhythmia. Any commercially released catheter deemed appropriate for the procedure may be used.
- b. Left atrial non-PVI ablations including but not limited to, ablation of linear lesions, complex fractionated electrograms or non-PV triggers will be treated as a primary endpoint failure. Ablation using RF in the left atrium will be treated as a primary endpoint failure.
- c. Additional right atrial ablations may be performed if clinically necessary.

13.5.6. Cardioversion

- a. Electrical or pharmacological cardioversion to sinus rhythm must be attempted following the PVI portion of the procedure if sinus rhythm wasn't restored.

13.5.7. Procedure Documentation

During the procedure the Investigator will document the following:

- Catheters used (i.e. Arctic Front Advance, Freezor *MAX* and Achieve Mapping Catheter, etc.)
- Minimum temperature for each cryoapplication
- Minimum esophageal temperature for each PV
- Duration of each cryoapplication
- Vein location for each cryoapplication (e.g. right superior PV)
- Use of phrenic nerve pacing or other phrenic nerve monitoring technique for each cryoapplication, specifically those cryoapplications surrounding the RS and RI PVs
- Demonstrated electrical block and, if real-time signals are available, time to isolation
- Adjunctive catheters, mapping or visualization devices, sedation type, procedure information, esophageal temperature, ACT, cardioversion use and fluoroscopy time will be collected

13.6. Hospital Discharge

At or shortly before hospital discharge, the following will be performed and collected:

- Adverse event assessment
- Review medications
- 12-lead ECG
- Review study requirements with the subject to help ensure compliance with follow-up procedures

Systemic anticoagulation with warfarin or a direct thrombin or Factor Xa inhibitor is recommended for at least two months following the AF ablation procedure, however the anticoagulation treatment will be at the Investigator's discretion according to established guidelines. Decisions regarding the continuation of systemic anticoagulation agents more than two months following ablation should be based on the subject's risk factors for stroke and not on the presence of AF.^{1,21,22}

13.7. Medications

It is recommended to discontinue the use of Class I and III antiarrhythmic medication by the end of the 90 day post-procedure blanking period. Up-titration of the dose is allowed only in the 90 day post-procedure blanking period.

Information regarding medications prescribed for anticoagulation or to treat atrial arrhythmias, including the medication name, purpose for use, start and stop dates, and route of administration, will be collected from subject enrollment through study exit.

13.7.1. Class I and III antiarrhythmic medication use after the 90 day post-procedure blanking period

- Subjects are allowed to remain on Class I or III antiarrhythmic medications at the historic maximum ineffective dose (on prior to the ablation procedure) after the 90 day post-procedure blanking period.
- Subjects may re-initiate, at any point during follow-up, a Class I or III antiarrhythmic medication that failed or was not tolerated prior to the ablation procedure at the same or lower dose.
- Initiation of a new Class I or III antiarrhythmic medication after the 90 day post-procedure blanking period will be treated as a primary endpoint failure.
- Remaining on a dose higher than the historic maximum ineffective dose (on prior to the ablation procedure) after the 90 day post-procedure blanking period will be treated as a primary endpoint failure.

All medications are permitted in the study with the exception of investigational drugs that may confound the study results.

13.8. Permissible Repeat Cryoablations

Pulmonary vein isolation using Arctic Front Advance following the same procedure described in 13.5 is allowed one time in the 90 day post-procedure blanking period. Right atrial ablations may be performed using any catheter deemed appropriate for the procedure.

Left atrial ablations of non-PV triggers, complex fractionated electrograms and ablation of linear lesions will be treated as a primary endpoint failure. Ablation using RF in the left atrium will be treated as a primary endpoint failure.

Repeat ablation procedures will be documented on an electronic case report form (eCRF). The subject's procedures and follow-up windows will continue based on the index cryoballoon ablation procedure date.

13.9. Cardioversions

Electrically and pharmacologically cardioverting the subject to sinus rhythm is allowed within the 90 day post-procedure blanking period at the discretion of the Investigator.

13.10. Scheduled Follow-up Visits

After receiving notice of completed study procedure, Medtronic will provide the target dates and windows for each visit to the center. Should a subject miss a visit or the visit fall outside the pre-specified window, a study deviation must be reported and the original follow-up schedule maintained for subsequent visits.

Data analyses include follow-up visits, regardless of whether the visit occurs within the window. Therefore, a late visit is preferred over a missed visit but must be accompanied by a deviation. Follow-up visit windows are listed in Table 8 and are based on days after the index ablation procedure.

Table 8: Follow-up Schedule

Occurrence/ Visit	Window (Calculated days after the ablation procedure)		
	Window Start	Target	Window End
Enrollment/Baseline	-30 days	-15 days	Day 0
Index Cryoablation Procedure	Day 0	Day 0	Day 0
6 week phone call	35 days	39 days	42 days
3 month office	91 days	91 days	121 days
6 month office	165 days	180 days	195 days
12 month office	365 days	365 days	395 days

The following information is required to be collected at the follow-up visits:

13.10.1. Six Week Phone Call

- Review medications
- Adverse event assessment
- Review symptoms suggestive of recurrent AF/AT/AFL

13.10.2. Three Month Office Visit

- Review medications
- Adverse event assessment
- Review symptoms suggestive of recurrent AF/AT/AFL
- 12-lead ECG
 - Send to the core lab
- Review the TTM system and begin transmitting weekly and upon symptoms

13.10.3. Six Month Office Visit

- Review medications
- Adverse event assessment
- Review symptoms suggestive of recurrent AF/AT/AFL
- 12-lead ECG
 - Send to the core lab
- 24h continuous monitoring with Holter
 - Send to the core lab
- SF-12 Health Survey and AFEQT Questionnaire

13.10.4. Twelve Month Office Visit

- Review medications
- Adverse event assessment
- Review symptoms suggestive of recurrent AF/AT/AFL
- 12-lead ECG
 - Send to the core lab
- 24h continuous monitoring with Holter
 - Send to the core lab
- SF-12 Health Survey and AFEQT Questionnaire

13.11. Unscheduled Office Visits

An unscheduled visit is defined as any unplanned cardiovascular-related office visit or early study exit at the study center that occurs between CIP required visits. If the subject exits the study early, an unscheduled office visit should occur. The following information is required to be collected at unscheduled follow-up visits:

- Review medications
- Adverse event assessment
- Review symptoms suggestive of recurrent AF/AT/AFL
- 12-lead ECG
 - Send to the core lab

13.12. Holter and TTM Management

Market-released Holvers will be distributed by a core lab to centers after activation has occurred. All subjects will wear a Holter in conjunction with their 6 and 12 month office visits. Holvers will then be sent back to the center after they have been worn by the subject. The core lab will be responsible for adjudication of atrial arrhythmias for the primary objective of the study. The core lab will manage maintenance, calibration and tracking of the Holvers.

Holter distribution logs will be provided to European centers. The logs must be maintained and updated when Holvers are received and returned to the core lab.

Market-released TTMs will be distributed by a core lab to centers after activation has occurred. All subjects will transmit weekly and symptomatic ECGs via the TTM system following their 3 month office visit. The TTM system will be sent back to the core lab at the end of the study. The core lab will be responsible for adjudication of atrial arrhythmias for the primary objective of the study. The core lab will manage maintenance, calibration and tracking of the TTMs.

TTM distribution logs will be provided to European centers. The logs must be maintained and updated when TTMs are received and returned to the core lab.

13.13. 12 lead Electrocardiograms

Market-released 12-lead ECG machines will be distributed by a core lab to centers after activation has occurred. All 12-lead ECGs starting with the one occurring at the 3 month office visit will be sent to the core lab. The 12-lead ECG machine will be sent back to the core lab at the end of the study. The core lab will be responsible for adjudication of atrial arrhythmias for the primary objective of the study. Copies of additional source documents may be requested. The core lab will manage maintenance, calibration and tracking of the 12-lead ECG machine.

12-lead ECG distribution logs will be provided to European centers. The logs must be maintained and updated when 12-lead ECG machines are received and returned to the core lab.

13.14. [REDACTED]

Follow Appendix B if the subject is enrolled in the sub-study [REDACTED]

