6.2. Endpoints

6.2.1. Primary Endpoints

1. Primary Efficacy: Demonstrate an acceptable efficacy success rate at 12 months after the pulmonary vein isolation (PVI) ablation procedure.

Treatment success is defined as freedom from treatment failure. Treatment failure is defined as any of the following components:

- Acute procedural failure
- Documented AF/AT/AFL on Holter/TTM/12-lead ECG after the 90 day blanking period
 - Minimum of 30 seconds on Holter/TTM and 10 seconds on 12-lead ECG
- A reablation for the treatment of recurrent AF/AT/AFL after the 90 day blanking period

- Class I or III antiarrhythmic drug (AAD) dose increase from the historic maximum ineffective dose (prior to the ablation procedure) or initiation of a new Class I or III AAD after the 90 day blanking period. Note: remaining on the same pre-ablation dose or decreased dose, or re-initiation of a previously failed or not tolerated Class I or III AAD after the 90 day blanking is not considered a failure.
- Ablation using RF in the left atrium

Blanking period is defined as the first 90 days after the index ablation procedure. Recurrences of atrial arrhythmias during the blanking period will not be counted in the determination of the first clinical failure for the primary endpoint. Within the blanking period, recurrent arrhythmias can be managed with antiarrhythmic drugs, cardioversion or one cryo re-ablation procedure of the pulmonary veins. Titration of Class I and III antiarrhythmic medications are allowed during the blanking period. Subjects are allowed to remain on Class I or III antiarrhythmic medications at the historic maximum ineffective dose (on prior to the ablation procedure) after the 90 day post-procedure blanking period.

Acute procedural failure is defined as:

- Inability to isolate all accessible targeted pulmonary veins (minimally assessed for entrance block and, where assessable, exit block) during the index procedure
- Left atrial non-PVI ablations including but not limited to, ablation of linear lesions complex fractionated electrograms or non-PV triggers

2. Primary Safety: Demonstrate an acceptable safety profile of the pulmonary vein isolation (PVI) ablation procedure.

A primary safety event is defined as a serious procedure-related or serious system-related adverse event including the following:

- Transient ischemic attack (within 7 days of ablation procedure)
- Cerebrovascular accident (within 7 days of ablation procedure)

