17.3. Primary Objectives

17.3.1. Primary Efficacy Objective

Demonstrate an acceptable efficacy success rate at 12 months after the pulmonary vein isolation (PVI) ablation procedure.

Hypothesis

The following hypothesis will be tested in a one-sided test at the 0.025 significance level:

Medtronic Confidential

Ho: PS \leq 40%

Ha: PS $>$ 40%

Where PS is the probability of treatment success at 12 months.

Endpoint Definition

Treatment success is defined as freedom from treatment failure. Treatment failure is defined as any of the following components:

- Acute procedural failure
- Documented AF/AT/ AFL on Holter/TTM/12-lead ECG after the 90 day blanking period
 - Minimum of 30 seconds on Holter/TTM and 10 seconds on 12-lead ECG
- A reablation for the treatment of recurrent AF/AT/AFL after the 90 day blanking period
- Class I or III antiarrhythmic drug (AAD) dose increase from the historic maximum ineffective dose (prior to the ablation procedure) or initiation of a new Class I or III AAD after the 90 day blanking period. Note: remaining on the same pre-ablation dose or decreased dose, or re-initiation of a previously failed or not tolerated Class I or III AAD after the 90 day blanking is not considered a failure. Subjects are allowed to remain on Class I or III antiarrhythmic medications at the historic maximum ineffective dose (on prior to the ablation procedure) after the 90 day post-procedure blanking period.
- Ablation using RF in the left atrium

Blanking period is defined as the first 90 days after the index ablation procedure. Recurrences of atrial arrhythmias during the blanking period will not be counted in the determination of the first clinical failure for the primary endpoint. Within the blanking period, recurrent arrhythmias can be managed with antiarrhythmic drugs, cardioversion or one cryo re-ablation procedure of the pulmonary veins. Titration of Class I and III antiarrhythmic medications are allowed during the blanking period.

Acute procedural failure is defined as:

- Inability to isolate all accessible targeted pulmonary veins (minimally assessed for entrance block and, where assessable, exit block) during the index procedure
- Left atrial non-PVI ablations including but not limited to, ablation of linear lesions, complex fractionated electrograms or non-PV triggers

Analysis Methods

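### Arrhythmia counts as failure from day 91, but TTM starts only at the 3-month visit (target day 91, window to day 121), and sections 13.11 and 13.13 conflict on core-lab ECGs before that visit

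*Protocol*

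**What the plan says.** **When failure starts to count.** Protocol 17.3.1: "Blanking period is defined as the first 90 days after the index ablation procedure". One failure component in 6.2.1 and 17.3.1 is "Documented AF/AT/AFL on Holter/TTM/12-lead ECG after the 90 day blanking period". The first countable day is therefore day 91.

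**When TTM starts.** The 3-month visit list (13.10.2) has: "Review the TTM system and begin transmitting weekly and upon symptoms". Section 13.12 likewise places weekly and symptomatic transmissions after that visit. Neither gives a study day.

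**When that visit happens.** Section 13.10: "Follow-up visit windows are listed in Table 8 and are based on days after the index ablation procedure". The row, read as window start, target and window end, is "3 month office 91 days 91 days 121 days". Out-of-window visits are tolerated: "a late visit is preferred over a missed visit but must be accompanied by a deviation". Nothing says when TTM begins for a subject who misses the visit.

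**Holter.** Worn only with the 6- and 12-month visits (13.12).

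**12-lead ECGs.** Section 13.13: "All 12-lead ECGs starting with the one occurring at the 3 month office visit will be sent to the core lab". Section 13.11 opens its list with "The following information is required to be collected at unscheduled follow-up visits"; the list includes a 12-lead ECG to be sent to the core lab, with no start date.

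**Who decides.** SAP 6.2.1 has the core lab adjudicate efficacy endpoints and takes events and onset dates from the core-lab and Clinical Events Committee adjudications.

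**The concern.** The period at risk is tied to a study day, but the start of surveillance is tied to an appointment. Between day 91 and the 3-month visit a subject can fail the primary endpoint with no TTM and no Holter in place. The text is also ambiguous about whether an ECG taken in that interval reaches the body that decides failure. Take a subject with an unscheduled visit in AF on day 98 and a 3-month visit on day 118. Under 13.11 the day-98 tracing goes to the core lab; under 13.13 it precedes the first one sent.

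Three features give this weight:

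- The trial is single-arm and unblinded and is tested against a fixed 40% goal, so an undocumented recurrence can only raise observed success.
- The length of the interval depends on when the visit is booked, so monitoring intensity can differ between subjects and sites.
- Protocol 17.3.1 cites the added weekly TTM as a reason for assuming 54% rather than the 59.3% literature average.

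Cardioversion is not a listed failure component, and restarting a previously failed drug is expressly not a failure. An early recurrence that ends before the visit may therefore trigger no other component.

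**Working it through.** **1. The plan's own figure.** SAP 7.1 uses an exact binomial test with 135 analysed subjects (150 less 10%), goal 40%, assumed success 54% and a pass at 66 or more successes.

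- P(X >= 66 | n = 135, p = 0.40) = 0.0224
- P(X >= 66 | n = 135, p = 0.54) = 0.899

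Both match the SAP. They do not depend on when TTM starts.

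**2. Length of the gap.** A visit on day v leaves days 91 to v - 1 uncovered, that is v - 91 days.

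| 3-month visit | Days without TTM or Holter |
|---|---|
| Day 91 (target) | 0 |
| Day 98 | 7 |
| Day 121 (window end) | 30 |
| Later than day 121 | more than 30 |
| Missed | no TTM start stated |

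Post-blanking days are 365 - 90 = 275. At the window end the gap is 30/275 = 10.9%. In weekly transmissions it is 30/7 = 4.3 of 275/7 = 39.3.

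**3. Which gap episodes bias the result.** The test uses the Kaplan-Meier estimate at day 365.

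- AF still present at the 3-month visit is caught by that visit's ECG.
- AF that recurs later can be caught by TTM, or by ECG and Holter at 6 and 12 months. Both kinds of failure are only dated later, which barely moves the day-365 estimate.
- An episode that begins and ends in the gap and is never documented at any time is lost, and the subject counts as a success.

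**4. Illustration of size.** The documents give neither the visit-date distribution nor the post-blanking hazard, so these inputs are assumptions: constant hazard over the 275 days, the same gap g for every subject, and a fraction m of first failures in the gap never detected later. The 66-of-135 rule stands in for the Kaplan-Meier bound.

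- Hazard at true success 40%: h = -ln(0.40)/275
- First failures in the gap: f = 1 - exp(-h g), giving 2.3 points for g = 7 and 9.5 points for g = 30
- Observed success: 0.40 + m f

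| Gap for all | m | Observed success | P(pass) |
|---|---|---|---|
| 0 days | any | 40.0% | 0.022 |
| 7 days | 10% | 40.2% | 0.026 |
| 7 days | 25% | 40.6% | 0.031 |
| 7 days | 50% | 41.2% | 0.042 |
| 30 days | 10% | 41.0% | 0.038 |
| 30 days | 25% | 42.4% | 0.075 |
| 30 days | 50% | 44.8% | 0.19 |

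With m = 0 there is no bias whatever the gap. The calculation treats every failure as one that depends on rhythm documentation after blanking. Acute procedural, reablation, drug and left atrial RF failures do not depend on TTM, so on that count the figures lean high. A hazard concentrated just after blanking would push them the other way.

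**The case against.** The plan already aims at the right day. The 3-month target is day 91, the sponsor sends each center its target dates, and an out-of-window visit must be reported as a deviation. Thirty days is the in-window extreme. This stands: the gap may be zero for many subjects, and the worst-case rows above should not be read as expected values.

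Section 13.11 already routes unscheduled-visit ECGs to the core lab, and 13.13 can be read as saying when routine submission begins. A reader might infer that no ECG before the 3-month visit can ever reach adjudication. The documents do not support that, because a site following 13.11 would send it. What remains is a conflict between two instructions.

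A reader might also infer that any AF occurring in the gap is scored as success. That is not so either: the 3-month ECG and some eight further months of monitoring give repeated chances to record it, after which the subject is a failure with a later date.

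Finally, the literature behind the 40% goal had no weekly TTM, so even a subject with the full 30-day gap has weekly monitoring that those studies lacked, and nothing links the 54% assumption to the four transmissions at issue. This also stands. It limits the importance of the gap, but it does not supply a TTM start date or reconcile 13.11 with 13.13.

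**Conclusion.** The point holds in a limited form. The endpoint opens on day 91 and TTM opens at a visit that may take place up to day 121 or later, with no start stated if the visit is missed. In-window, the gap runs from 0 to 30 of 275 days (0 to 10.9%). Sections 13.11 and 13.13 give different answers for an unscheduled ECG recorded in that interval.

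Any bias favours the device, and it comes only from gap episodes that end before the visit and are never documented again. The documents do not allow its size to be derived. Under the stated assumptions the chance of passing at a true 40% rises from 0.022 to 0.026-0.042 with a 7-day gap for everyone, and to 0.038-0.19 if every visit fell on day 121. It would be tempting to conclude that the trial's type I error is materially inflated. The documents do not show this, since they give neither the visit dates nor the share of recurrences never seen again. The change is worth making because it is cheap and removes a one-directional risk. Sample size and stated power are unaffected.

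**What to change.** - Issue the TTM before day 91, for example at hospital discharge, and start weekly and symptomatic transmissions on day 91 whatever the visit date, including when the 3-month visit is late or missed.
- Reword 13.13 so that every 12-lead ECG recorded from day 91 after the index procedure, at any scheduled or unscheduled visit, goes to the core lab, consistent with 13.11.
- Align 13.10.2, 13.12 and Table 7 with these two rules.

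**Cost.** Wording changes in a few places. TTM units are held longer per subject, and up to about four more weekly transmissions per subject are read. Observed success may be slightly lower, because recurrences that would have gone unrecorded are counted. The sample size (150 treated, 135 analysed), the power of 0.899 and the analysis method stay as they are.
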